#### **5.1.7 Allowed Interventions**

For ethical and legal reasons, all participants will be permitted whatever care they would receive as part of their medical coverage provided by Medicare and any other supplemental insurance they have.

#### **5.2 Usual Medical Care**

This group will receive whatever care they would normally receive during the study period. Usual medical care for chronic back pain typically includes continued use of

medications (mostly non-steroidal anti-inflammatory medications) and visits to primary care physicians, physical therapists, and complementary medicine providers. In order to adequately describe the care that has been provided, we will collect information from the GH electronic medical record describing any imaging and other tests ordered, medications (prescribed or recommended use of over the counter), written advice given, notes on activity level, exercise, referrals to physical therapy, complementary therapies, medical specialists, any surgeries performed) as recommended by Somerville et al.

We think this is the best control group for this study because it is the only one that can answer the practical question of whether Tai Chi, when added to usual medical care, is beneficial for relieving cLBP and associated dysfunction. Guidelines for optimal care of older adults with cLBP do not exist and we therefore cannot use guideline-driven care. No clear package of standard care exists and thus, careful documentation of usual medical care, including the need for specialist care and for surgeries will be clearly documented.

A substantial fraction of persons with chronic back pain rely on self-care, only occasionally seeking professional help. In order to minimize disappointment at not being randomized to Tai Chi, participants in the Usual Medical Care group will receive a gift from the study, which will be a stainless steel water bottle with the Kaiser Permanente logo. Compensation has helped maintain high response rates (i.e., close to 90%) from control group participants in our previous trials, but we suspect that a gift will be more appreciated than cash in this population. However, we will follow the guidance from our patient partners.

### **5.3 Attention Control**

Our attention control is designed to match on attention and time in the standard tai chi intervention (i.e., 2x/week of 12 week 60 minutes) and credibility (health education topics of value to seniors that they think could impact their back pain). Each of the 60 minute sessions will include interesting didactic material along with questions and a brief discussion. The sessions will be presented by students in the University of Washington nurse practitioner training program, pharmacy interns and the Study Investigators, geriatric fellows and other expert colleagues when available. We will have a Research Assistant attend the classes to provide continuity and they will be selected for their interest and ability to work with this age group. The didactic material has been selected from a variety of medical (e.g., UptoDate; various Kaiser Permanente Washington guidelines), scientific (e.g., PubMed, National Institutes of Health, CDC), and community sources (e.g., National Caregiver Association).

**Table 3: Health Education Classes**

Week	1 st Class	Topic	2 nd Class	Topic
1	1	Healthy Living	2	Back Pain
2	3	Nutrition	4	More Nutrition
3	5	Using Meds Safely	6	Flu/Pneumonia Prevention
4	7	Osteoporosis	8	Fall Prevention

5	9	Brain Health	10	Heart Health and Stroke
6	11	Safe Driving	12	Diabetes
7	13	Communicating with your physician	14	Skin Health
8	15	Caregiving	16	Osteoarthritis
9	17	Housing Options	18	Depression
10	19	Bladder Problems	20	Sleep
11	21	Social Support	22	Stress Reduction
12	23	Footwear	24	Wrap Up

To minimize the likelihood that the seniors will achieve improvement in pain and functional status, we placed those topics we thought most relevant to chronic pain for many older adults(e.g., depression, osteoarthritis, sleep, stress reduction) toward the end of the intervention. We will also inquire about any changes they made in their life as a result of the classes.

## **6. DESCRIPTION OF STUDY VISITS AND OUTCOME MEASURES**

Table 4 presents the schedule of evaluations, while Table 3 further displays the physical and questionnaire assessments.

**TABLE 4. Schedule of Evaluations**

ASSESSMENT	Screening/ Baseline	Tai Chi Classes/ Attention Control	12/26- Wk	52- Wk
Informed Consent	x/			
Demographics [baseline]	/x			
Medical History [some screening, some baseline]	x/x			
Inclusion/exclusion criteria [screening]	x/		x	x
Physical Assessments	x		x	x
Questionnaire with Outcome Measures [see Table 3]	x		x	x
Enrollment/Randomization	/x			
Class Attendance		x		
Home Practice Logs		x		
Adherence to Tai Chi Protocol/Attention Control Protocol		x		
Adverse events		x	x	x
Qualitative discussion [subset of participants]		x	x	x

### **6.1 Screening Evaluation**

The screening evaluation will be performed by telephone with KPW members who have returned a statement of interest or called our toll-free project number with their contact information or with members of the public who have responded to various forms of outreach. A Research Specialist will phone those members to answer

questions, obtain oral consent for an initial telephone eligibility screen and determine preliminary eligibility using a computer program to guide the interviewer through a series of screening questions based on the final inclusion and exclusion criteria. The screening process will end with documentation in a database of either preliminary eligibility or ineligibility. Individuals whose responses suggest they are provisionally eligible and who are interested in the feasibility RCT will then be scheduled to come to a group in-person assessment in a conference room at a large Kaiser Permanente Washington clinic. They will receive information about the details of the conference room location ahead of time. Individuals who were deemed provisionally eligible more than 10 days in advance of the scheduled baseline visit will be recontacted by phone to make sure that their pain levels were sufficiently high that they remain eligible.

## **6.2 Enrollment, Baseline and Randomization**

Study participants will be enrolled in the study when they have completed their written informed consent, their baseline physical assessments, baseline questionnaire, and been randomized (see Section 4.4 for further details). Documentation of randomization will take place by computer. All participants will be enrolled within two weeks of the first class of each cohort. We will use the recommendations made by the NIH Task Force on Research Standards for Chronic Low Back Pain for studies of chronic low back pain. and for specific baseline information, including a core set of baseline outcome domains, and appropriate PROMIS measures for these domains Baseline information will include sociodemographic characteristics (gender, age, race, ethnicity, education level, employment status, and marital status), back pain history (e.g., years since first episode of back pain, duration of current episode) and other factors that are prognostic of resolution of back pain (e.g., number of pain sites and patient expectations of treatment outcome). The core set of recommended outcomes includes physical function, low back pain intensity, pain interference, depression, sleep disturbance, and catastrophizing. The Baseline Schedule of assessments is shown in Table 3 and the specific outcome assessments are described further in Section 6.2.4.

## **6.3 Blinding**

Research Specialists who collect data on physical measures will be masked to treatment group at all time points. Participants, the instructor and the many study staff will necessarily be aware of group assignment.

## **6.4 Follow-up Visits**

To maximize response rates, reminder letters will be sent before each follow-up visit. The contents of the in-person follow-up visits (12, 26 and 52 week) is shown in Table 2. While participants are provided an opportunity to complete their assessments in a group format (with instructions not to discuss their group assignment), physical assessments (Short Physical Performance Battery, Four Square Step Test, Gait Speed) will take place in a private room adjacent to the group area. The follow-up questionnaire will be administered using either a study tablet computer or a paper questionnaire, whichever the participant prefers. Questions about experiences with specific aspects of the Tai Chi intervention that might cause participants to think differently about their outcomes will be asked at the end of an interview, after all other outcomes are

assessed. We will attempt to obtain outcome data from all participants in the trial. The Research Specialist, masked to study group, will be present and available to answer any questions that might arise while the participant is completing the follow-up questionnaire. Our patient partners will be asked about the value of the group format at follow-up and the likelihood we can maintain our masking with multiple participants in a room. If this is believed unfeasible, we will schedule visits in the same location (GH clinic classroom) for one individual at a time.

The NIH Task Force on Research Standards for Chronic Low Back Pain made recommendations for a core set of baseline outcomes. These measures include many of the key outcome domains recommended for us used in trials of chronic low back pain. We will therefore include all of these in our questionnaire along with a few others. Table 3 summarizes the measures, with the NIH Task Force recommendations being shaded in blue. Relevant additional secondary measures of interest for virtually all older adults include scales assessing fear of falling and measures of balance.

We will modify our outcome measures in consultation with our patient partners in the Administrative Year prior to the RCT. Because older adults have a variety of symptoms, we might, for example, include the MYMOP measure, which allows patients to assess progress on their own desired outcomes from health care. Careful attention will be paid to ensure that the questionnaire is not too burdensome for older adults. We would aim for approximately 20 minutes for the follow-up questionnaires.

**TABLE 5:Content of Baseline and Follow-up Assessments  
SOURCES OF DATA FOR BACK TAI CHI TRIAL**

MEASURES	Baseline	12-Wk	26-Wk	52-Wk
BASELINE INFORMATION				
Patient characteristics (age, gender, ethnicity, race, employment status, education, height, weight, smoking status, excessive use of drugs or alcohol) (NIH Task Force Research Standards); education	x			
Back pain history (pain duration, leg pain, other pain sites, low back operation, use of selected treatments, work loss due to back pain, disability status, catastrophizing, fear avoidance)	x			
Expectations and knowledge of Tai Chi/Health Education	x			
CORE SET OF OUTCOMES FOR BACK PAIN STUDIES				
* Back dysfunction (24-item Roland Morris Disability Questionnaire-RMDQ)	x	x	x	x
* Low back pain intensity (0-10 numerical rating scale)	x	x	x	x
Pain interference (4-items PROMIS)	x	x	x	x
Pain Interference and enjoyment of life (2-items PEG)	x	x	x	x
Physical Function (4-items PROMIS)	x	x	x	x

Depression (4-items PROMIS)	x	x	x	x
Anxiety Screener (GAD-2)	x	x	x	x
Sleep disturbance (4-items PROMIS)	x	x	x	x
Patient Global Impression of Change (7 item scale)		x	x	x
Participant Disposition (see Section 6.4.iv)		x	x	x
TREATMENT-RELATED INFORMATION				
Adverse events		x	x	x
Perceptions of Tai Chi & HE classes, including instructors		x	x	
Adherence to assigned treatment, including home practice		x	x	x
Willingness to participate in a RCT of Tai Chi with an Attention Control (Cohort 1)	x			
POTENTIAL CONFOUNDERS				
Use of co-interventions (medications, other treatments, etc.)	x	x	x	x
Daily exercise and job-related activity	x	x	x	x
MEASURES FOR FALLS AND BALANCE				
Short Physical Performance Battery (balance, gait speed, chair stand)†	x	x	x	x
Four Step Square Test†	x	x	x	x
Fear of Falling	x	x	x	x

\*Co-Primary Outcome Measures

† Physical Assessment

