#### **MASKING**

All persons collecting outcome information (i.e., assessors) will be masked to each participant's group assignment.

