### **iv. Documentation of intervention fidelity**

In addition to identifying any general problems with our implementation procedures or with specific aspects of the treatment protocols, we will determine the level of adherence to class attendance and home practice in the standard and maintenance time periods. Class attendance will be documented by a Research Specialist who will attend all of the classes to manage study-related processes and allow the Tai Chi instructor to pay full attention to her students. We will also collect data from students on home practice. At the first class, we will give participants weekly logs to record their home practice throughout the 36-week intervention period (We will ask that they bring their logs to class once a week and to give them to the Research Specialist). We have used this process in our recent yoga RCT with moderate success. In addition, we will ask participants during the 12, 26 and 52-week follow-up interviews about the number of days they practiced during the prior week and the average number of minutes they practiced on those days. This method of collecting data on home practice has worked well in our previous RCTs. Finally, we will assess treatment fidelity by reviewing the information we collected evaluating the ability of the Tai Chi instructor to adhere to the treatment protocols and the extent to which participants were able to grasp what they were taught and translate it into skillful Tai Chi movements.

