## **10. DATA COLLECTION, QUALITY CONTROL AND CONFIDENTIALITY**

## **10.1 Data Collection Forms**

Eligibility information will be collected directly in a computer assisted telephone interviewing database. Baseline and follow-up questionnaires will be self-report on paper forms or, if necessary, via telephone interview. Masked assessors (trained Research Specialists) will collect data on the physical assessments using paper forms.

Individual records will be identified by a unique study identification number.

Records linking study ID with participant names or other identifying information that may be needed for follow-up interviews, class attendance, etc. will be kept separate from the study data and will be accessed only by study team members on a need-to-know basis. All study files will be kept in a locked filing cabinet. Computer files will be secure and password protected.

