## **10.2 Data Management**

We will employ our time- tested procedures for interview data collection and quality control, scanning self-administered forms or using double key entry verification of paper forms or to minimize data collection errors during baseline and follow-up interviews. If possible, self-report interview data will be collected in –person and inspected for completeness before the participant leaves to minimize errors. We will employ our standard quality control procedures to ensure that data collection is proceeding smoothly, electronic data are password protected and paper forms are stored in locked filing cabinets to ensure confidentiality of information.

We will implement procedures to ensure that all data collection processes are proceeding smoothly. These procedures will ensure that randomization is proceeding as planned, recruitment is on schedule, data collection forms are accurately entered into databases, the database is storing data correctly and that data can be accurately transferred and retrieved as needed. We will develop a relational database to track information on every stage of recruitment, randomization, class attendance, and outcomes assessment so we can report patient flow automatically and in an integrated fashion using standard, automated reports. All data system processes will be thoroughly tested prior to the start of recruitment.

All questionnaire databases will contain range and logic checks. Participant attendance information collected during the classes will be double key entered into a computer database that also contains logic checks. Prior to recruitment, all data systems will be tested with imaginary participants. Data will be examined for completeness using computer programs developed specifically for that purpose. In addition, we will test all analytic programs to ensure that the analyses are accurate. Computer files with participant names will be password protected with access restricted to staff using this information to recruit participants, contact class participants or obtain follow-up data, and interact with any patients reporting adverse events. Any paper data forms, such as homework logs, identifiable only by unique study ID numbers, will be kept in locked filing cabinets. Finally, all analysis data files will be password protected. Full data backup procedures are performed nightly, with partial data back-up throughout the day.

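### The masking promised for the follow-up physical tests is not protected and may fail, because a masked Research Specialist helps with a questionnaire that contains arm-revealing items.

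*Protocol*

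**What the plan says.** **What is promised.** The Precis states: "All persons collecting outcome information (i.e., assessors) will be masked to each participant's group assignment". Section 6.3 is narrower but firm: "Research Specialists who collect data on physical measures will be masked to treatment group at all time points". Section 10.1 names the role: "Masked assessors (trained Research Specialists) will collect data on the physical assessments using paper forms".

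**What happens at follow-up.** Under Section 6.4, "The Research Specialist, masked to study group, will be present and available to answer any questions" that come up during the questionnaire. Table 5 puts "Adherence to assigned treatment, including home practice" on it at 12, 26 and 52 weeks, and perceptions of the Tai Chi and health-education classes at 12 and 26 weeks. Section 7.1 adds a question on harm from Tai Chi classes or home practice at all three visits. Section 6.4.iii adds open-ended questions about the interventions, also at all three.

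**Who else may see or hear the answers.** Section 10.2 wants self-report data collected in person, if possible, and "inspected for completeness before the participant leaves to minimize errors"; it does not say by whom. Section 10.1 allows telephone administration if necessary.

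**Who else holds the same job title.** A Research Specialist randomises participants (Section 4.4). Section 5.1.6.iv says: "Class attendance will be documented by a Research Specialist who will attend all of the classes".

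**Existing safeguards.** Participants complete their own forms (Section 3). Section 6.4 places questions on the Tai Chi experience after the other outcomes, does the physical tests in a private room, tells participants not to discuss assignment, and falls back on one-at-a-time visits if masking in a group looks unworkable.

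**The concern.** A masked staff member is assigned to help with a form whose treatment items can reveal the arm. If that person, or whoever checks the form or conducts a telephone interview, later tests the same participant, the test is no longer masked. The plan has no step that prevents this and none that would detect it.

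The outcomes at stake are the staff-rated ones: the Short Physical Performance Battery, gait speed and the Four Square Step Test. A rater who knows the arm can influence timing, encouragement and scoring. Assessor masking does much less for the co-primary outcomes (Roland scale and pain), which participants who know their arm report themselves. The physical tests are where the promise has most of its value.

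Section 9.1 describes the study as a thorough evaluation of procedures before a larger trial. As planned, it would report masked assessment without evidence that the masking held.

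**Working it through.** The plan gives no figure to reproduce, so the check is mainly a comparison of sections.

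**1. Does the form reveal the arm?** Yes, through the answers.

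| Item | 12 wk | 26 wk | 52 wk | Source |
|---|---|---|---|---|
| Adherence, home practice | yes | yes | yes | Table 5 |
| Perceptions of classes | yes | yes | no | Table 5 |
| Harm from Tai Chi | yes | yes | yes | Section 7.1 |
| Open-ended intervention questions | yes | yes | yes | Section 6.4.iii |

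In cohort 1 there are only two arms, 19 and 19 (Section 4.4), so any answer that shows or rules out Tai Chi identifies the arm.

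**2. Is a masked person near those answers?** Yes. Section 6.4 describes the questionnaire helper as masked. The completeness checker (Section 10.2) and the telephone interviewer (Section 10.1) are not described either way.

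**3. Is the helper the physical tester?** Not stated. Both are masked Research Specialists, and nothing joins or separates the two tasks.

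**4. Do the safeguards block this route?** Only in part. Asking the Tai Chi questions last is justified by its effect on the participant's own answers. If the other outcomes include that visit's physical tests, it protects those tests. It does nothing for the next visit if the same specialist returns. The private room, the instruction not to discuss assignment and the one-at-a-time fallback deal with talk between participants, not with sight of the form.

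**5. How far could carry-over reach?** Knowledge gained at 12 weeks can affect the tests at 26 and 52 weeks; knowledge gained at 26 weeks can affect those at 52. The ceiling is 78 participants x 2 visits = 156 visits, assuming full attendance.

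**6. Illustration on an assumed input.** Let p be the chance that a visit reveals the arm to a masked staff member. The documents give no value. With independent visits, the chance of at least one disclosure is 1 - (1 - p)^3 over three visits and 1 - (1 - p)^2 over the two visits that precede a later test.

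| Assumed p | Three visits | of 78 | First two visits | of 78 |
|---|---|---|---|---|
| 2% | 5.9% | 4.6 | 4.0% | 3.1 |
| 5% | 14.3% | 11.1 | 9.8% | 7.6 |
| 10% | 27.1% | 21.1 | 19.0% | 14.8 |
| 20% | 48.8% | 38.1 | 36.0% | 28.1 |
| 50% | 87.5% | 68.2 | 75.0% | 58.5 |

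For example, at p = 10%: 1 - 0.9^3 = 0.271, and 0.271 x 78 = 21.1; 1 - 0.9^2 = 0.19, and 0.19 x 78 = 14.8. A disclosure harms a test only if the person who learned the arm then does that test, so these are upper figures for any given p.

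**The case against.** The strongest reply is that no actual breach is shown.

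- The helper is not said to be the tester. The questionnaire may be completed in the group area while the tests run in an adjacent private room, and the protocol speaks of several Research Specialists. This stands.
- Help is on request. A question about a Roland or PROMIS item reveals nothing, and Table 5 does not suggest that the form differs by arm. Unmasking needs someone to read or hear a treatment answer. This stands, so it would be wrong to infer that everyone who helps with or checks the form learns the arm.
- The completeness check applies only if possible, and nothing gives it to a masked assessor. True, but nothing keeps it from one either.
- Section 6.3 already requires masked testers, which by implication excludes class and randomisation staff for the participants they dealt with. This largely stands; what is missing is an explicit rule. Section 10.3.1 leaves detailed procedures to a Manual of Operations that is not among the documents.
- Carry-over needs the same specialist to learn the arm, remember it 14 weeks (12 to 26) or 40 weeks (12 to 52) later, and test that participant again. No document says this will happen, and none prevents it.
- The consequence is limited. The tests are not co-primary, Section 3 sets no effectiveness hypotheses, and masking is not among the four feasibility outcomes in the Precis. It would be speculation to say that the procedure will be declared feasible and carried forward.

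**Conclusion.** The stated masking is not protected and may fail. The plan gives a masked specialist a task that brings that person close to arm-revealing answers, leaves the checker and the telephone interviewer undefined, does not explicitly place the physical tests before the treatment items at follow-up, and plans no record of unmasking.

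Two stronger conclusions are tempting. One is that masking cannot hold across the three visits. That would need a per-visit disclosure chance near 1 and the same person helping and testing; the documents establish neither. The other is that all 78 x 3 = 234 follow-up visits are compromised. That is the number of possible visits, not of exposures. The carry-over ceiling is 156, and the number actually affected is unknown.

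The conclusion assumes that the masked helper, the checker or the interviewer may also test, which the documents leave open. The point is worth acting on because the remedy is cheap and the study exists to test procedures. It does not touch the co-primary outcomes.

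**What to change.** Amend Sections 6.3, 6.4 and 10.2, with a matching line in 10.1 on telephone interviews:

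1. At each follow-up visit, do the physical tests before the questionnaire is opened.
2. Put the adherence, home-practice, class-perception and Tai Chi harm items in a separate final section. Help with that section, its completeness check and any telephone administration of it come only from existing staff who already know the allocation.
3. State that specialists who randomised participants or staffed classes in a cohort do not do that cohort's follow-up tests. This makes explicit what Section 6.3 implies.
4. Have the assessor record at each visit whether the arm became known, and report the result as a feasibility finding.

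The cost is wording, form layout and a rota among existing staff, with somewhat less freedom in visit order and staffing. No new visits are needed. Item 4 would also supply the unmasking rate that is now missing.
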